11.3. Vital Signs

Systolic blood pressure (mmHg), diastolic blood pressure (mmHg), heart rate (bpm), respiratory rate (breaths per minute) and temperature (degree Celsius) will be measured at different timepoints as per the schedule of events (Section 1.3) in the Protocol.

Actual values and changes from baseline in vital sign measurements will be summarized by treatment.

Note temperature will be reported in centigrade. Any conversions required will be as follows:

Temperature (in °C) = 5/9 (Temperature [in °F]-32).

All vital signs will be provided in data listings.

11.4. ECG

The ECG parameters include heart rate, PR, RR, QRS, QT, and corrected QTcF intervals.

Analysis of drug related QT/QTc interval changes relative to serum PK concentrations will be conducted on all dose regimens. The principles of this analysis follow the statistical methods described by Garnett et al. (Garnett, 2018). All ECG recordings will be in triplicate and compliant with the correct recording and manual adjudication of ECG in thorough QT/QTc studies. The ECG analyses will be based on adjudicated selected triplicates from each time point. The average of the triplicate ECG readings at the time points collected will be calculated, and changes from pretreatment baseline values will be assessed by each cohort. The average of the triplicate ECG readings will be used to derive QT/QTc at all visits (*i.e.* both pre- and post-baseline visits). An outlier analysis will be performed that will summarize the absolute count, frequency and percentage of participants who meet any of the following outlier criteria at each visit by cohort:

- QT, QTcF interval > 450 msec
- QT, QTcF interval > 480 msec
- QT, QTcF interval > 500 msec
- QT, QTcF interval increases from baseline > 30 msec

This document is confidential.

- QT, QTcF interval increases from baseline > 60 msec

Actual values and change from baseline of these average ECGs will be summarized by treatment.

All ECG parameters, including all single ECG measurements, but also the mean value and overall ECG evaluation will be provided in data listings.

If a participant shows an abnormal ECG, additional safety recordings (including the use of 5- or 12-lead Holter equipment) may be made, and the abnormality will be followed to resolution. The 24-hour Holter ECG recording results will be provided in data listings.

If deemed necessary, a separate concentration-QT analysis may be performed by Alexion. The concentration-QT analysis is not within the scope of this SAP.

11.5. Physical Examination

A full physical examination will be performed at different timepoints as per the schedule of events (Section 1.3) in the Protocol.

A symptom-driven physical examination of relevant body systems may be performed at other times, at the Investigator's discretion.

Physical examination data will be listed.

11.6. Injection or Infusion Site Evaluation

Subcutaneous injection/infusion or IV infusion-site evaluations will be performed at the time points specified in the schedule of events (Section 1.3) in the Protocol. Injection/infusion site reactions will not be recorded as AEs unless deemed clinically significant.

The severity (grade) of the injection/infusion site evaluation will be summarized by treatment and visit/timepoint.

Injection/infusion site evaluation data will be listed.

This document is confidential.

12. Immunogenicity

The population used for immunogenicity analyses will be the Immunogenicity Set (IGS).

The immunogenicity analyses will include an analysis of ADAs using descriptive statistics. The results will summarize the difference between healthy non-Japanese participants and participants of Japanese descent.

Whole blood samples will be screened for ADAs that bind to ALXN1820. If the screen is positive, the sample will be analyzed using a confirmatory ADA assay and the titer of confirmed positive samples will be reported.

The actual date and time (24-hour clock time) of each sample will be recorded. Refer to Section 1.3 of the Protocol for the schedule of activities indicating when the ADA samples are taken for each cohort.

ADA and Neutralizing Antibodies (NAb) data reporting:

- Incidence, titer, duration, time to detection, pre-existing ADA;
- PK concentration or parameter by immunogenicity response;
- PD response by immunogenicity response;
- Individual data listing or spaghetti plots with ADA category overlaid.

For ADA categories and participants, summary of individual plots of PK, PD, ADA and NAb titer time course to better understand the clinical impact of immunogenicity at a subject level.

This document is confidential.

13. Interim Analyses

Interim assessments will be performed as follows:

- An assessment of all available PK/PD data will be performed when all participants in Cohorts 4 and 5 reach Day 29. These data will be used to project the exposure and duration of properdin and CAP activity inhibition (not to exceed 70 days) at the highest single dose planned in the study (Cohort 7) and the highest multiple dose in the study (Cohort 10).
- CAP activity will be continuously analyzed and will be used to estimate the time of CAP activity returning to baseline for each individual participant based on PK/PD modeling.

The interim analysis is outside the scope of this SAP.

This document is confidential.

14. Changes from Analysis Planned in Protocol

Not Applicable.

This document is confidential.

15. Reference List

This document is confidential.

16. Quality Control

SAS programs are developed to produce output such as analysis data sets, summary tables, data listings, figures or statistical analyses. An overview of the development of programs is detailed in Syneos Health Developing Statistical Programs SOP (3907).

Syneos Health Developing Statistical Programs SOP (3907), Conducting the Transfer of Biostatistical Deliverables SOP (3908) and the SAS Programming and Validation Plan describes the quality control procedures that are performed for all SAS programs and output. Quality control is defined here as the operational techniques and activities undertaken to verify that the SAS programs produce the output by checking for their logic, efficiency and commenting and by review of the produced output.

Syneos Health SOP Pharmacokinetic and Related Data Analysis (3913) describes the process for the interaction between the Biostatistics and Pharmacokinetics departments for the analysis of pharmacokinetic and pharmacodynamic data.

This document is confidential.

ALXN1820-HV-101_Final_Version_SAP_2.0_28 Nov2022_XJ_SS_JW

Final Audit Report

2022-11-30

Created:	2022-11-30
By:	[REDACTED]
Status:	Signed
Transaction ID:	[REDACTED]

"ALXN1820-HV-101_Final_Version_SAP_2.0_28Nov2022_XJ_S S_JW" History

-  Document created by [REDACTED]
2022-11-30 - 1:16:47 PM GMT- IP address: [REDACTED]
-  Document emailed to [REDACTED] for signature
2022-11-30 - 1:18:01 PM GMT
-  Document emailed to [REDACTED] for signature
2022-11-30 - 1:18:01 PM GMT
-  Document emailed to [REDACTED] for signature
2022-11-30 - 1:18:02 PM GMT
-  Email viewed by [REDACTED]
2022-11-30 - 1:18:52 PM GMT- IP address: [REDACTED]
-  Signer [REDACTED] entered name at signing as [REDACTED]
2022-11-30 - 1:19:26 PM GMT- IP address: [REDACTED]
-  [REDACTED] verified identity with Adobe Acrobat Sign authentication
2022-11-30 - 1:19:28 PM GMT
-  Document e-signed by [REDACTED]
Signing reason: I am the author
Signature Date: 2022-11-30 - 1:19:28 PM GMT - Time Source: server- IP address: [REDACTED]
-  Signer [REDACTED] entered name at signing as [REDACTED]
2022-11-30 - 1:20:20 PM GMT- IP address: [REDACTED]

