^a For injection-site reactions, a cohort and/or the study will be suspended when ≥ 3 participants are observed. If all but 1 affected participant show signs of recovery (at least to Grade 1), cohort and study continuation can then proceed. If ≥ 2 participants remain at Grade 2 after the minimum data review period, the period of observation should be extended for up to 168 hours. If all but 1 affected participant show sign of recovery (at least to Grade 1), cohort and study continuation can then proceed. If ≥ 2 affected participants remain at Grade 2 after the first 168-hour extension period, the SRC will make the decision to either prolong further the observation period up to a maximum of another 168 hours, or suspend the remainder of the cohort and study. At the end of the second extension period, if all but 1 participant show sign of recovery (at least to Grade 1), cohort and study continuation can then proceed. If, however, ≥ 2 affected participants remain at Grade 2, cohort and study will be suspended.

^b A substantial amendment may include an amendment to the protocol, the ICF, or other study-related documents as appropriate.

Abbreviations: ALT = alanine aminotransferase; AST = aspartate aminotransferase; CTCAE = Common Terminology Criteria for Adverse Events; ECG = electrocardiogram; Hb = hemoglobin; ICF = informed consent form; IV = intravenous; NA = not applicable; SOC = System Organ Class; SRC = Safety Review Committee; ULN = upper limit of normal.

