7.4. Visit Windows

If there are multiple planned assessments for any study procedure at a given time point the latest non-missing value will be used for summarization, unless specified otherwise. Unscheduled assessments will be listed and will be used to flag baseline visit if this is the last non-missing assessment before the first dose of study drug, but unscheduled assessments will not be included in the summarization.

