The summary tables will include the number of participants and the number of events. Percentages will be based on the number of participants. Repeat AE summary tables will be created to display percentages based on the number of events. For summaries by SOC and PT, a participant will be counted once at the SOC level and once at each PT within the SOC level.

For summaries by SOC, PT and maximum Common Terminology Criteria for Adverse Events (CTCAE) grading, a participant will be counted once at the highest CTCAE grading for which the event occurred at the SOC level and the highest CTCAE grading for each unique PT within that SOC level. Therefore, participants may only contribute once to each PT and once to each SOC level.

The summaries presenting frequency of AEs by SOC and PT will be ordered by overall descending frequency of SOC and then, within a SOC, by overall descending frequency of PT.

The following tables will be provided:

- An overall summary of the number and percentage of participants reporting TEAEs, serious TEAEs (TESAEs), TEAEs leading to death, TEAEs leading to withdrawal of study drug, TESAEs leading to withdrawal of study drug, TEAEs by relationship, TESAEs by relationship and TEAEs by CTCAE grade;
- TEAEs overall by system organ class and preferred term;
- TEAEs by maximum CTCAE grading, overall and by system organ class and preferred term;
- TEAEs by strongest relationship to study medication, overall and by system organ class and preferred term;
- TEAEs overall by system organ class;
- TEAEs overall by preferred term;
- Related TEAEs (TERAEs), overall by preferred term;
- TESAEs overall by system organ class and preferred term;
- TESAEs by maximum CTCAE grading, overall and by system organ class and preferred term;
- TESAEs by strongest relationship to study medication, overall and by system organ class and preferred term;

Only TEAEs (or TESAEs, as applicable) will be included in the summary tables, however we will generate separate listings for treatment-emergent and non-treatment-emergent AEs. Additional listings will be provided for deaths, serious adverse events, AEs resulting in withdrawal from the study and AEs resulting in study drug withdrawal.

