All summaries will be based on results in SI (standard international system of units) units and will be output in the order listed above.

Toxicity grading following the NCI CTCAE grades version 5.0 will also be derived for laboratory variables where applicable (see list below). Note, where gradings require investigator/clinical input, this will not be considered and only the numeric criteria will be used for the assignments. If this results in the criteria for more than one grade being met, the highest (worst) CTCAE grade will be assigned. For creatinine only, the criteria based on the upper limit of normal (ULN) will be used (changes compared to the baseline value will not be used), e.g., CTCAE defines Grade 1 as $> \text{ULN} - 1.5 \times \text{ULN}$ or $> 1 - 1.5 \times \text{baseline}$. Only the $\text{ULN} - 1.5 \times \text{ULN}$ criterion will be used (and not the baseline criterion).

This document is confidential.

The following parameters are CTCAE gradable:

- **Hematology:** Absolute neutrophil count (neutrophil), total leukocytes (Leukocytes), hemoglobin (only do the grading for Anemia, no grading for Hemoglobin increased), platelet count, Lymphocyte.
- **Coagulation:** International normalized ratio.
- **Chemistry:** Alanine aminotransferase albumin, alkaline phosphatase, aspartate aminotransferase, total bilirubin, creatinine, gamma-glutamyl transferase, glucose (only do the grading the Hypoglycemia, no grading for Hyperglycemia), creatine kinase.

Actual values and changes from baseline (screening) in hematology, coagulation, clinical chemistry, and urinalysis will be summarized by treatment.

Shift tables for hematology, clinical chemistry and coagulation from baseline CTCAE toxicity for each visit and to the maximum CTCAE grade on treatment for each parameter will be provided. Participants with both a non-missing baseline and at least one non-missing post-baseline grade will be included in the shift tables. Unscheduled data will be included in the worst case across all scheduled and unscheduled visits after the first dose of study treatment. This means that if there are CTCAE grades derived from both unscheduled and scheduled visits data per test per participant then the highest grade will be summarized.

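### SAP 11.6 tabulates injection/infusion site grade only by time point, so the table can understate how many participants had a site reaction; a worst-grade-per-participant summary should be added

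*SAP*

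**What the plan says.** SAP 11.6 (Injection or Infusion Site Evaluation) plans two outputs. The first is a table: "The severity (grade) of the injection/infusion site evaluation will be summarized by treatment and visit/timepoint". The second is a listing: "Injection/infusion site evaluation data will be listed". The text names no per-participant maximum. The same section limits what reaches the adverse event tables: "Injection/infusion site reactions will not be recorded as AEs unless deemed clinically significant".

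Elsewhere the SAP does count participants at their worst. For adverse events (SAP 11.1), in the tables by grade, "a participant will be counted once at the highest CTCAE grading for which the event occurred". For CTCAE-graded laboratory tests (SAP 11.2), "Unscheduled data will be included in the worst case across all scheduled and unscheduled visits after the first dose of study treatment".

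SAP 7.4 (Visit Windows) sets the general rule that "unscheduled assessments will not be included in the summarization", although such assessments are listed. The footnotes to the protocol's Schedule of Activities (Section 1.3) require a site reaction to be followed until it has fully resolved, which can be after the last scheduled post-dose evaluation at 24 h.

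**The concern.** Two questions a reader will ask about local tolerability are how many participants had a site reaction and how severe the worst one was. A table with one row per evaluation time answers neither directly. Reactions that occur at different times, or after different weekly doses, fall in different rows. The largest row may then be smaller than the number of participants affected, while adding the rows can count one participant several times.

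The adverse event tables close the gap only for reactions judged clinically significant, a term the documents do not define. For all other site reactions, SAP 11.6 is the only planned summary.

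ALXN1820 is formulated for subcutaneous use, tolerability is in the primary objective, and the weekly-dose cohorts are where repeat-dose local tolerability is observed. At stake is whether the final report contains a prespecified participant-level incidence and worst severity of site reactions.

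**Working it through.** The documents give no figure to reproduce on this point. The check asks how far a by-time table determines the number of participants affected.

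**Inputs from the documents**
- Active participants per cohort: 6 (Protocol Table 2).
- Scheduled post-dose site evaluations per dose: end of injection/infusion, 30 min (1 h in Cohorts 6 and 7), 2, 4, 8, 12 and 24 h, so 7 (Protocol Tables 4, 6, 7, 9 and 10).
- Rows: 7 for a single dose; 5 × 7 = 35 in Cohorts 8 and 9; 3 × 7 = 21 in Cohort 10.

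**Bounds (no assumptions)**

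Let r_j be the number of participants at Grade 2 or higher in row j, and N the number of distinct participants ever at that grade among scheduled evaluations. Then max(r_j) ≤ N ≤ min(6, Σ r_j).
- Rows 1, 1, 1: N is anywhere from 1 to 3.
- Rows 2, 2: N is anywhere from 2 to 4.
- A single non-zero row of 3: N = 3 exactly.

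Three participants who each react at a different time give three rows of 1/6 (17%), whereas the participant-level incidence is 3/6 (50%).

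**How often the largest row falls short**

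Assume exactly 3 reactors, one reaction each, with independent timing. Duration and timing are assumptions.

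| Setting | Chance that some row shows all 3 | Chance that none does |
|---|---|---|
| Single dose, each seen at one random evaluation | 7 × (1/7)³ = 7/343 | 1 − 0.020 = 0.980 |
| Single dose, random start, lasting up to 3 evaluations | 103/343 | 1 − 0.300 = 0.70 |
| Single dose, random start, lasting to 24 h | 1 (all are in the 24 h row) | 0 |
| QW × 5, random dose, random start, lasting to 24 h | 5 × (1/5)³ = 1/25 | 1 − 0.04 = 0.96 |
| QW × 5, same participants react after every dose, lasting to 24 h | 1 | 0 |

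In the second line, all three overlap when their start times span at most 2 steps. There are 5 windows of three starts (27 triples each), less 4 overlaps of two starts (8 triples each): 135 − 32 = 103.

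A simulation that lets the number of reactors vary (each of 6 reacts with probability 0.3 or 0.5, on one random dose, for 1, 2, 4 or 7 consecutive evaluations) gives the chance that no row reaches 3 when at least 3 reacted:
- Single dose: 94–96% (1 evaluation), 63–74% (2), 0% (4 or 7).
- QW × 3: 72–100%.
- QW × 5: 88–100%.

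With probability 0.5 and QW × 5, a mean of 3.0 participants are affected and the mean largest row is 1.1 to 1.6.

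**Evaluations after 24 h**

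The schedules show no post-dose site evaluation column beyond 24 h. Later follow-up of an unresolved reaction would then be unscheduled and, under SAP 7.4, listed but not summarized. In the weekly cohorts the next pre-dose evaluation is scheduled, so a reaction still present a week later would be seen there. A peak between 24 h and that visit may appear in no row.

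**The case against.** The strongest reply is that the important reactions are already covered. A reaction judged clinically significant is recorded as an adverse event and enters the SAP 11.1 table of "TEAEs by maximum CTCAE grading, overall and by system organ class and preferred term". The listing shows every evaluation, and with 8 participants per cohort a count by hand is feasible. Both points stand, and they make this a modest reporting gap. They do not remove it. Reactions below the undefined significance threshold have no worst-grade summary, and at full enrolment the listing would hold about 1,120 scheduled post-dose records (7 × 8 × 7 + 2 × 8 × 35 + 1 × 8 × 21 = 392 + 560 + 168).

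A second reply is that the high percentages depend on the timing chosen. This also stands. A reader might infer that the table does understate incidence. The documents support only that it can: they give no data on duration or recurrence, and where reactions overlap one row captures every reactor.

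A reader might also infer that the table undermines the stopping rule, since Protocol Table 21, footnote a, says: "For injection-site reactions, a cohort and/or the study will be suspended when ≥ 3 participants are observed". The documents do not support that. Table 21 counts adverse events related to the drug and also depends on recovery. The Investigator and the Safety Review Committee make dosing decisions during the study (Protocol 6.6), not from the final SAP tables. A worst-grade row would match only the rule's first count.

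Two further points stand. The primary endpoint does not name site evaluation, and Protocol 9.4.2 plans no summary of it, so SAP 11.6 already goes beyond the protocol. SAP 7.1 also refers to table shells that are not part of the documents reviewed; they might contain a worst-grade row. If so, the SAP text should say so.

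**Conclusion.** The point holds as a gap in the final reporting of local tolerability. No table described in the SAP text gives the participant-level incidence or worst grade of all injection/infusion site reactions, although the SAP uses that method for adverse events and CTCAE-graded laboratory tests. Each by-time row is a lower bound, and this follows from the table's structure without any assumption.

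The size of the shortfall does rest on assumptions. For 3 reactors of 6, the chance that no row shows all 3 ranges from 0% to about 98%. The shortfall is most plausible in Cohorts 8, 9 and 10, where reactions may follow different doses, and it vanishes there too if the same participants react after every dose with reactions lasting to 24 h. The exclusion of unscheduled evaluations adds a separate route by which a late peak may go unsummarized. No dosing decision is affected, and the listing allows the count to be recovered by hand.

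**What to change.** Add to SAP 11.6:

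> Each participant will also be counted once at the worst post-dose grade, including unscheduled evaluations, per dose (multiple-dose cohorts) and over all doses; the number and percentage by worst grade will be presented by cohort and treatment arm.

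Keep the by-time table, which shows onset and resolution. The mention of unscheduled evaluations is needed because SAP 7.4 would otherwise exclude them. It would also help to state how this table relates to site reactions recorded as adverse events, since a clinically significant reaction would appear in both.

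The cost is SAP wording and one extra descriptive table from data already collected. Study conduct, sampling and the stopping rules do not change.
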